10.7.1.2 General considerations and descriptive analysis

The following relates to secondary and exploratory objectives 5, 11 and to any other descriptive analysis conducted in the study.

For the descriptive analysis of continuous variables, the number of observations, number of missing values, mean, standard deviation, median, lower (1st) and upper (3rd) quartiles, as well as 5th and 95th percentiles will be presented. For categorical variables, the numbers, and percentages of observations for each of the categories will be presented in descriptive analysis. The number of patients and percentages with missing data for each variable will be reported. Further details on methodology will be provided in the SAP.

In the descriptive analysis, the total number of patients at risk and the number of events for each study outcome in the exposed to anifrolumab and SLE SOC comparator groups will be tabulated both before and after PS based adjustments [5, 89]. Descriptive tables will also include the SOC treatments received, number of flares in 6 months prior to study entry and time since last flare by exposure status. Covariate balance will be assessed by examining the distribution of variables in the cohorts and estimating standardised differences for each variable between the anifrolumab-exposed and the comparator cohort. In case large differences in standardised differences are present, modifications to the time-conditional propensity score or to the matching algorithm will be considered. Modification could include using the alternative model for fitting the PS model (Cox regression vs conditional logistic regression) or implementing a calliper when selecting the time-conditional matched comparators in step 9. Further details will be provided in the SAP:

The measures of study outcomes, with associated 95% CI, will be estimated for the exposed to anifrolumab and unexposed groups.

In all regression analyses, guidelines for appropriate fitting of any logistic or cox regression model recommend a minimum of ten outcome events per term (where term may be any linear covariate, non-linear predictor, or interaction term). In the primary analysis, including the primary and secondary objectives, if sufficient outcome events are not available, regression results should be interpreted with caution with regards to bias and precision. In addition, descriptive statistics of the occurrence and duration of all infections leading to hospitalisation, in moderate/severe SLE

patients initiating anifrolumab and in comparable moderate/severe SLE patients who do not initiate anifrolumab (exposed to SLE SOC), will also be provided (objective 11). For this, the number, proportion of patients, median time to recurrent serious infection, duration of hospitalisation for each recurrent serious infection and death will be tabulated for both treatment cohorts.

10.7.1.3 Estimation of crude incidence rates

The following relates to primary and secondary objectives 1, 3, 6, 8 and 9 and exploratory objective 11.

Using the exposure definition mentioned in Section 10.3.1, the crude IRs for each outcome (malignancy and serious infections) within the relevant sub-cohort will be expressed as number of cases per 1,000 patient-years at risk. Only the event under study in each of the sub-cohorts will be considered. For example, a patient with an incident serious infection event who subsequently is newly diagnosed with a malignancy event will contribute with both event groups of interest to the study.

Crude cumulative IRs of serious infection will be calculated over these time periods of interest - 30, 180, and 365 days from index date. For malignancy outcome, the time periods used for calculating crude cumulative IR will be: 1-year, 3-year and 5year since the start of follow-up after the 12-month latency period.

The crude cumulative IR will be calculated as the number of malignancies during the cumulative interval of interest, divided by the total person-years at risk in the period. It will be presented per 1000 person-years at risk, with the associated 95% CI. In addition, plots of cumulative incidence function will also be presented, calculated using the Nelson-Aalen non-parametric method, over the study period for all the outcomes under consideration.

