Descriptive analysis will be performed in the study sub-cohorts exposed to anifrolumab and unexposed to anifrolumab. Baseline characteristics will be presented before and after PS matching. For baseline characteristics collected as continuous variables, the number of observations, number of missing values, mean, standard deviation, median, lower (1st) and upper (3rd) quartiles, as well as 5th and 95th percentiles will be presented. For categorical variables, the numbers, and percentages of observations for each of the categories and numbers and percentages of missing values will be presented in descriptive analysis. Incidence rates and cumulative incidence, with associated 95% confidence intervals (CIs) will be presented for all relevant study objectives.

For the comparison of the study sub-cohorts exposed to anifrolumab and unexposed to anifrolumab within the study cohorts, HRs, with associated 95% CIs will be estimated for each relevant outcome. Unbalanced variables after matching will be used as covariates in the outcome models.

For the primary objectives, meta-analysis will be conducted to combine results from individual data sources. The meta-analysis for the primary objectives will be performed using results from all study countries for which comparative analysis was successfully performed. Prior to conducting the meta-analyses, heterogeneity across the study countries will be assessed. Country-level logHRs and their standard errors will be entered in a random-effect inverse-variance model. Data source-specific results and the overall combined estimate will be presented in forest plots including effect size and 95% CI for each study country included in the analysis.

Milestones

Planned study milestone dates are dependent on protocol endorsement date. Therefore, any deviation from the protocol approval date will trigger changes in all subsequent dates. Study progress will be reported in the periodic safety update reports. One joint interim report will be provided for both serious infection and malignancies outcomes, and the last interim report for malignancies only will be provided. Final study reports will be provided separately for serious infections and malignancies. Tentative study milestones are listed below:

PRAC approval	31 August 2023
Registration in the EU PAS register	30 November 2023
Start of data collection	31 May 2025
Interim report 1 (serious infections & malignancies)	31 May 2027

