10.3.1.2.1 FOLLOW-UP FOR THE MALIGNANCY COHORT

For the primary and secondary objectives related to malignancies, follow-up will start after a 12months latency period after the index date (Figure 7). The latency period will be used to accommodate for the period between the exposure to drug and the diagnosis of cancer [72]. During this period, a malignancy diagnosis will not be considered an outcome of interest because of the low probability of being related with anifrolumab or other SOC new exposure. Additionally, a 12month at risk window after the end of the treatment episode will capture malignancies diagnosed soon after drug discontinuation to avoid possible bias caused by not being able to pinpoint the discontinuation date more accurately. Thus, follow-up ends at the end of treatment episode plus 12 months, occurrence of the first malignancy or at any of the **censoring** events (i.e., loss to followup for disenrollment/de-registering, death, or end of the study period/date of data extraction), whichever occurs first.

[figure not shown]

Figure 7 Follow-up assessment for the malignancy cohort (main analysis) Abbreviations: SLE, systemic lupus erythematosus; SOC, standard of care

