10.3.1.2.2 FOLLOW-UP FOR THE SERIOUS INFECTION COHORT

For the serious infection primary and secondary objectives, follow-up starts at index date and ends at the end of the treatment episode (Figure 8), occurrence of a serious infection or at any of the **censoring** events (loss to follow-up for disenrollment/de-registering, death, or end of the study period/date of data extraction), whichever occurs first.

For the exploratory objective, follow-up ends at the end of treatment episode or any of the censoring events: loss to follow-up for disenrollment/de-registering, death, or end of the study period/date of data extraction, whichever occurs first.

Figure 8 Follow-up assessment for the serious infection cohort (main analysis) Abbreviations: SLE, systemic lupus erythematosus; SOC, standard of care

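### The cumulative incidence plots are to be calculated by Nelson-Aalen with death censored, so they will show a cumulative hazard and overstate risk, slightly at the horizons the protocol names

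*Protocol*

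**What the plan says.** Section 10.7.1.3 opens: "The following relates to primary and secondary objectives 1, 3, 6, 8 and 9 and exploratory objective 11". It therefore covers the two primary descriptive objectives, 1 and 3. It specifies three things.

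- Crude incidence rates per 1,000 patient-years, with this rule: "Only the event under study in each of the sub-cohorts will be considered".
- A crude cumulative IR at 30, 180 and 365 days for serious infection, and at 1, 3 and 5 years after the latency period for malignancy. "The crude cumulative IR will be calculated as the number of malignancies during the cumulative interval of interest", divided by the person-years at risk in that interval.
- As an addition, over the whole study period and for every outcome: "plots of cumulative incidence function will also be presented, calculated using the Nelson-Aalen non-parametric method".

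Death is a censoring event in both cohorts. Section 10.3.1.2.2 (serious infection) lists "loss to follow-up for disenrollment/de-registering, death, or end of the study" period among the censoring events, and section 10.3.1.2.1 (malignancy) has the same list. Section 10.3.2.2 makes one exception: a death within 30 days of a recorded infection is itself a serious infection event.

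The abstract (section 5) goes further than plots: "Incidence rates and cumulative incidence, with associated 95% confidence intervals (CIs) will be presented for all relevant study objectives". No competing-risk estimator is named anywhere in the protocol.

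**The concern.** A cumulative incidence function is the probability that the event has occurred by time t. The Nelson-Aalen estimator targets the integrated hazard, which is not a probability and is larger than the corresponding risk. When deaths are censored, the curve also describes a population in which nobody dies before the event, whereas in the real cohort death rules the event out. Both errors push the curve upward.

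The cumulative IR does not fill the gap. It is events over person-years, so it is a rate. If the abstract's cumulative incidence with 95% CI is to be delivered, the only method the protocol offers for it is Nelson-Aalen. In a safety study, a reader will take absolute risk, and the absolute difference between groups, from these curves. Section 10.7.1.3 names the estimator itself, so this is a stated method and not a detail left to the statistical analysis plan.

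**Working it through.** The protocol states no cumulative incidence figure, so there is nothing to reproduce. The check compares what each estimator targets, using the protocol's own rates and constant hazards.

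**Inputs**
- Malignancy rate λ = 6.31 per 1,000 person-years; serious infection rate λ = 39.8 per 1,000 person-years (section 10.5.2, SLE populations).
- Planning hazard ratio 1.5 (section 10.5.2).
- Named horizons: section 10.7.1.3, as above.
- Longest possible serious infection follow-up: 11 March 2022 (earliest launch, Table 3) to 31 May 2025, or 3.22 years.
- Mortality μ: not in the document. Assumed to be 5 to 30 per 1,000 person-years.

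**Formulas**
- Nelson-Aalen target: H = λt.
- Risk with deaths censored: 1 − exp(−H).
- Cumulative incidence with death competing (Aalen-Johansen target): λ/(λ+μ) × [1 − exp(−(λ+μ)t)].

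**Worked example: malignancy, 5 years, μ = 0.005.** H = 0.00631 × 5 = 3.155%. Cumulative incidence = (0.00631/0.01131) × [1 − exp(−0.05655)] = 3.067%. Excess: 0.088 points; 3.155/3.067 − 1 = 2.9%.

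**Results at the background rate (range over μ = 5 to 30 per 1,000)**

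| Outcome, time | Nelson-Aalen | True cumulative incidence | Relative excess | Points |
|---|---|---|---|---|
| Serious infection, 30 days | 0.327% | 0.326% | 0.2-0.3% | 0.001 |
| Serious infection, 180 days | 1.961% | 1.940-1.928% | 1.1-1.7% | 0.02-0.03 |
| Serious infection, 365 days | 3.980% | 3.892-3.844% | 2.3-3.5% | 0.09-0.14 |
| Serious infection, 3 years (plots only) | 11.94% | 11.17-10.77% | 6.9-10.8% | 0.77-1.17 |
| Serious infection, 3.22 years (end of plots) | 12.82% | 11.93-11.48% | 7.4-11.7% | 0.88-1.34 |
| Malignancy, 1 year | 0.631% | 0.627-0.620% | 0.6-1.8% | 0.004-0.011 |
| Malignancy, 3 years | 1.893% | 1.861-1.794% | 1.7-5.5% | 0.03-0.10 |
| Malignancy, 5 years | 3.155% | 3.067-2.885% | 2.9-9.4% | 0.09-0.27 |

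With the rate multiplied by 1.5, the excess is 0.19-0.26 points for serious infection at 365 days and 0.17-0.44 points for malignancy at 5 years.

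**Separating the two causes.** With no deaths at all, H against 1 − exp(−H) gives 2.0% for serious infection at 365 days, 6.1% at 3 years (0.1194/0.1125) and 1.6% for malignancy at 5 years. Most of the low-end serious infection figure is thus the hazard-for-risk substitution. The rest comes from competing death and depends on the assumed μ.

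**Difference between groups, equal mortality, hazard ratio 1.5.** For serious infection at 365 days the plotted gap is 5.970 − 3.980 = 1.99 points, against a true gap of 5.781 − 3.892 = 1.89 down to 5.710 − 3.844 = 1.87. For malignancy at 5 years it is 4.732 − 3.155 = 1.58, against 4.565 − 3.067 = 1.50 down to 4.295 − 2.885 = 1.41.

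**Simulation check** (400,000 patients, μ = 10 per 1,000). Malignancy at 5 years: Nelson-Aalen 3.18%, complement of Kaplan-Meier 3.13%, Aalen-Johansen 3.06%. Serious infection at 3.22 years: 12.84%, 12.05% and 11.87%. The ordering agrees with the formulas.

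**The case against.** The strongest reply is that little depends on these plots. Section 10.7.1.3 makes incidence rates the main measure for objectives 1 and 3 and introduces the plots as an addition. That stands. A reader might infer that the primary descriptive results are overstated, but the text does not support this: events over person-years and Cox hazard ratios do not use Nelson-Aalen.

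A reader might also take 7-11% as the size of the problem for serious infection. That figure belongs to about 3 years, which is not a named horizon. The serious infection study period ends on 31 May 2025, so only patients indexed by 31 May 2022 can reach 3 years. For the whole of 2022, Table 27 expects 14 initiators in Denmark, 15 in Germany and fewer than 10 each in France and Spain, out of 1,435, and Table 3 puts the Spanish launch at May 2023 (to be confirmed). The tail of the exposed curve rests on a handful of patients.

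Nor is the error all due to censored deaths, as shown above. For serious infection, deaths within 30 days of a recorded infection already count as events, so only the remaining deaths compete. A claim that the bias differs between groups because mortality differs also has no support, since the document gives no mortality by group.

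Two defences do not succeed. The authors may intend 1 − exp(−H), or may intend to build Aalen-Johansen from Nelson-Aalen increments. The text says neither, and the first would still censor deaths. Section 10.7 leaves derivations and presentation to the statistical analysis plan, but here the protocol has already fixed the estimator. Calling events over person-years a cumulative IR is only a matter of terminology, because the quantity is openly defined.

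**Conclusion.** The point holds as a minor one. Followed as written, section 10.7.1.3 plots a cumulative hazard under the name of a cumulative incidence function, and the error is always upward. It reaches the plots and any cumulative incidence with 95% CI taken from them for the abstract's promise, and nothing else.

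At the background rates, the overstatement at the longest named horizons is about 0.1 percentage points for serious infection (365 days) and at most about 0.3 for malignancy (5 years). These sizes assume constant hazards and mortality of 5 to 30 per 1,000 person-years. For serious infection, that mortality should be read as deaths not already counted as outcome events. The direction of the error depends on none of these assumptions.

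**What to change.** In section 10.7.1.3, replace the Nelson-Aalen sentence as follows.

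- **First-event outcomes:** estimate cumulative incidence by Aalen-Johansen, with 95% CI, at the horizons already listed. The competing event is death not already counted as an outcome event. For the malignancy sub-types, other first malignancies compete as well, because section 10.3.2.1 considers only the first malignancy.
- **Recurrent hospitalised infections (objective 11):** a first-event estimator does not fit. Use a mean cumulative count that accounts for death, and label it as such.
- **Leave unchanged:** the incidence rates, the interval-specific events per person-year, and the Cox models.

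Relabelling the plots as cumulative hazards would make them correct, but would leave the abstract's cumulative incidence without a method. The full change costs a sentence or two and standard software. It needs no new data, since dates of death are available in all four data sources, and it does not touch the sample size.

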10.7.1.4 Comparative analysis

The following relates to primary and secondary objectives 2, 4, 7, 10 and exploratory objective 12.

For objectives 2, 4, 7 and 10, cox proportional hazard regression models will be used to estimate the HR within the matched populations with a robust sandwich covariance matrix to account for the same patient contributing anifrolumab exposed person-time and SOC-exposed person-time. HRs and the corresponding 95% CIs will be reported. The proportional hazard assumption will be verified for each study exposure. The final objective-specific outcome models for the PS-matched cohort analyses will include any variables found to be imbalanced after the PS matching.

For objective 12, based on the descriptive analysis and on the availability of sufficient patients across data sources, a comparative analysis will be conducted to compare the average risk (hazard) of recurrent infections (up to 4th serious infection only) in patients initiating anifrolumab and in comparable moderate/severe SLE patients who do not initiate anifrolumab (exposed to SLE SOC). Further details on the methodology will be available in SAP.

10.7.1.5 Confounding variables

All confounders listed previously in Section 10.3.3, will be assessed once for each patient at their index dates.

10.7.1.6 Meta-analyses

In addition to data source level analyses, results will also be combined in a meta-analysis. Metaanalysis will be performed only for the primary study objectives. The meta-analysis will be performed using aggregated data from all study countries, assuming the country-specific analyses are available for pooling. Prior to conducting the meta-analysis, heterogeneity across the study countries will be assessed using:

- Cochran's Q test (significance level: 0.1). Q is calculated as the weighted sum of squared differences between individual studies and the pooled value across data sources.
- The I² statistic (0% to 40%: might not be important; 30% to 60%: may represent moderate heterogeneity; 50% to 90%: may represent substantial heterogeneity; 75% to 100%: considerable heterogeneity). I² is calculated as follows:

$$I^2 = \left(\frac{Q - df}{Q}\right) \times 100\%$$

Where Q is Cochran's statistic and 'df' is its degrees of freedom. The I^2 is a statistic that estimates the percentage of variance in effects attributable to study heterogeneity rather than sampling error.

• τ^2 statistic: Utilises the Q value to calculate the excess variation across data sources

If high levels of heterogeneity are found to exist, the study design and characteristics in the included local studies will be reviewed and the possible source of heterogeneity discussed. The country-level logHRs and their standard errors will be entered in a random-effect inverse-variance model. Data source-specific results and the overall combined estimate will be presented in forest plots including effect size and 95% CI for each study country included in the analysis. In a sensitivity analysis, the meta-analysis will be done using a fixed-effect model.

Further details regarding the meta-analysis will be presented in the SAP.

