- 9) To estimate the incidence of the first occurrence of opportunistic serious infections, other serious infections, pneumonia (overall), fatal and non-fatal pneumonia (separately) in moderate/severe SLE patients initiating anifrolumab and in comparable moderate/severe SLE patients who do not initiate anifrolumab (exposed to SLE SOC).
- 10) To compare hazard rates of the first occurrence of opportunistic serious infections, other serious infections, pneumonia (overall), fatal and non-fatal pneumonia (separately) in moderate/severe SLE patients initiating anifrolumab versus comparable moderate/severe SLE patients who do not initiate anifrolumab (exposed to SLE SOC), when feasible (i.e., if sample size allows).

Exploratory objectives

The following objectives pertain to the serious infection outcomes:

- 11) To estimate the incidence of recurrent infections leading to hospitalisation, in moderate/severe SLE patients initiating anifrolumab and in comparable moderate/severe SLE patients who do not initiate anifrolumab (exposed to SLE SOC).
- 12) To compare the hazard rates of recurrent infections leading to hospitalisation in moderate/severe SLE patients initiating anifrolumab and in comparable moderate/severe SLE patients who do not initiate anifrolumab (exposed to SLE SOC), when feasible.

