10.2 Setting

The study will include longitudinal patient-level data from large data sources in four countries in Europe: Denmark, France, Germany, and Spain. These data sources have been selected based on the results from feasibility assessment. Details of the feasibility and rationale for database selection are provided in Section 10.4.

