10.3.2.1 Malignancies

As the **primary outcome**, new malignancies will include any first haematological, solid, or skin malignancies registered in the databases in the follow-up period. Benign tumours will not be included. Incident malignancies, identified by a diagnosis listed in Table 15, will be defined as new malignancies; subsequent malignancy diagnoses will not be considered.

As **secondary outcomes**, specific types of the first malignancy diagnosis will be considered. Three groups of malignancies will be considered as separate outcomes (Table 15, objectives 6 and 7): haematological, solid, and skin cancers. Within each outcome, the frequency of specific malignancies⁵ (Table 15) (e.g., for haematological malignancies: non-Hodgkin's lymphoma, leukaemia, etc.; for solid cancers: lung, thyroid, breast, etc.) will be described.

If a patient is diagnosed with two or more malignancies during the study period, the follow-up time up to the occurrence of the first malignancy will be considered.

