• Missing information might also vary between the data sources. Whenever applicable, missing information will be reported.

• When the outcome for a specific analysis has less than five cases/observations, the specific result and other potentially related results may not be reported as such in all the included databases, as it could lead to the identification of patients. This may be a potential limitation for analyses that require stratification, such as the detailed number of specific malignancies. Furthermore, minimum and maximum values cannot be reported.

• For data sources with data only available for recent years, the date of SLE diagnosis or the first SLE SOC prescription may be left-censored. This might result in misclassification of SLE duration or previous SLE SOC duration. However, in this study, no differential misclassification is assumed within country-specific data sources.

• All relevant variables for the definition of the PS and for further adjustment will be included in the analyses. However, information on individual covariates may not be available in all databases, such as body mass index, smoking or alcohol consumption. This and possible unknown confounding variables may result in residual confounding of the study results.

Exposure assessment

• Anifrolumab is a novel drug. Thus, the drug uptake in the countries and populations covered in the data sources may be slow at the beginning of the study period and is likely to increase closer to the end of the study.

• Anifrolumab is not indicated for the treatment of severe, active central nervous system lupus or severe, active lupus nephritis [29]. These conditions were not considered as exclusion criteria to capture all patients that might be using anifrolumab in real-world context (even if not indicated for). Clinical manifestations related with lupus nephritis and central nervous system lupus will be included as part of the severity algorithm and PS and thus, patients exposed to anifrolumab and to SLE SOC will be matched on these conditions.

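### Objectives 7 and 10 are never pooled, so they yield up to 32 country-level hazard ratios and no cross-country estimate, and outside France these say little

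*Protocol*

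**What the plan says.** The protocol's meta-analysis section (10.7.1.6) sets the scope: "Metaanalysis will be performed only for the primary study objectives". The abstract says the same, and Table 2 marks a meta-analysis for objectives 2 and 4 only. That section leaves only further details to the SAP, so an SAP that follows the protocol cannot add pooling for the secondary comparisons.

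Those comparisons are nevertheless modelled in every data source. Section 10.7.1.4 states: "For objectives 2, 4, 7 and 10, cox proportional hazard regression models will be used to estimate the HR within the matched populations". Section 10.2 names "large data sources in four countries in Europe: Denmark, France, Germany, and Spain".

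- Objective 7 covers three groups (section 10.3.2.1): "haematological, solid, and skin cancers". It carries no feasibility condition.
- Objective 10 covers five outcomes (section 9.1): "opportunistic serious infections, other serious infections, pneumonia (overall), fatal and non-fatal pneumonia (separately". It applies "when feasible (i.e., if sample size allows".

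Two passages bear on sparse results. Section 10.7.1.2 gives a guide of ten events per model term and asks for caution when events are too few, for secondary objectives as well as primary. Section 10.9 adds: "When the outcome for a specific analysis has less than five cases/observations, the specific result and other potentially related results may not be reported".

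**The concern.** The study-size argument in section 10.5.2 needs all four sources pooled to reach 80% power for the composite outcomes. The sub-types are subsets of those composites and have fewer events, yet they are analysed in four separate pieces. No summary is named, so nothing says which hazard ratio answers a secondary objective.

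These outcomes matter to the study's purpose. Section 8.3 names pneumonia as the commonest cause of fatal infection, and section 10.9 expects haematological cancers to be the most frequent type. If the answer is in effect French, it also inherits French ascertainment. Section 10.9 says that malignancies there are captured only through hospitalisation, and that hospital intravenous antimicrobials are captured only for expensive drugs. Denmark, the only source using a population-based cancer registry, expects 183 exposed patients. The heterogeneity statistics and forest plot that would show whether the sources agree are planned for the primary outcomes only.

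**Working it through.** **Inputs.** Exposed patients, malignancy / serious infection (Table 8): Denmark 183 / 89, France 2,695 / 1,005, Germany 216 / 126, Spain 412 / 216, total 3,506 / 1,435. Rates, follow-up and matching (section 10.5.2): 6.31 per 1,000 person-years over 5 years, 39.8 per 1,000 over 2 years, 1:3. The protocol gives no sub-type shares, so 10%, 30% and 50% are assumptions; a 100% share is an upper bound.

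**The plan's own figure.** A 20,000-run simulation used the Table 13 country shares, source HRs with mean 1.5 and SD 0.2, inverse-variance random-effects pooling (DerSimonian-Laird) and two-sided p<0.05. It gave power 0.79 at 3,195 exposed (malignancy) and 0.80 at 1,312 (infection), against 0.80 stated. The inputs are therefore read as intended.

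**Count.** (3 + 5) outcomes x 4 sources = 32, of which 3 x 4 = 12 are unconditional and 5 x 4 = 20 depend on sample size. Outside France: 8 x 3 = 24. France's share of exposed patients: 1,005/1,435 = 70% and 2,695/3,506 = 77%.

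**Upper bound for the three small sources.** Give each sub-type the whole composite rate λ with follow-up f.

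Events D = n(1 − exp(−λ·HR·f)) + 3n(1 − exp(−λ·f))

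Power = Φ(√(0.25 × 0.75 × D) × ln HR − 1.96) (Schoenfeld)

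Example, Spain, infection, HR 1.5: D = 216 × 0.1125 + 648 × 0.0765 = 24.3 + 49.6 = 73.9. Power = Φ(√(0.1875 × 73.9) × 0.405 − 1.96) = Φ(−0.45) = 0.33.

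| Source | Events, malignancy | Power, HR 1.5 | Events, infection | Power, HR 1.5 |
|---|---|---|---|---|
| Denmark | 26 | 0.14 | 30 | 0.16 |
| Germany | 30 | 0.16 | 43 | 0.21 |
| Spain | 57 | 0.27 | 74 | 0.33 |

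The largest value for HR 2 is 0.77 (Spain, infection). A Wald approximation is slightly kinder: for Spain, infection, SE = √(1/24.3 + 1/49.6) = 0.248 and Φ(0.405/0.248 − 1.96) = 0.37. At an assumed 30% share the three sources have 8-17 malignancy or 9-23 infection events, and Schoenfeld power of 0.07-0.13 for HR 1.5.

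**France, same formula, HR 1.5.** At shares of 50%, 30% and 10%, events are 190, 114 and 38 (malignancy) and 176, 107 and 36 (infection). Power is 0.68, 0.47, 0.19 and 0.64, 0.44, 0.18.

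**Withholding.** Exposed sub-type events at HR 1 are binomial with p = 1 − exp(−λ·share·f). For infection at 30%, p = 1 − exp(−0.0398 × 0.3 × 2) = 0.024. The chance of fewer than five exposed events is about 0.94 in Denmark, 0.82 in Germany and 0.41 in Spain. At 10% it is 0.97 or more in all three.

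**What pooling adds.** France alone and the pooled random-effects estimate were simulated on the same footing (Table 8 counts, SD of HR 0.2).

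- HR 2, 10% share: power 0.55 to 0.64 (infection) and 0.57 to 0.64 (malignancy).
- HR 2, 30% share: no material gain; pooled power is 0.91 and 0.90, and France alone is about the same.
- HR 1.5, 30% share, infection: the 95% CI runs from HR ÷ 1.50 to HR × 1.50 for France alone, and the factor falls to 1.43 pooled.
- HR 1.5, pooled: power 0.67 or less at a 50% share, so no sub-type at or below that share reaches 80%.

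**Follow-up.** Mid-period entry from the Table 27 initiations, the Table 3 end dates and no discontinuation allow at most about 2.2 years after latency (malignancy) and 0.9 years (infection), not 5 and 2. Events then fall to roughly 40-60% of those above, and the best small-source power for HR 1.5 at the full composite rate is 0.16.

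**The case against.** The restriction is stated consistently in three places, so it is a deliberate scope choice and not a contradiction. The document also anticipates sparse data: objective 10 is conditional on sample size, section 10.7.1.2 asks for caution, and section 10.9 foresees withheld results. All of this stands. The condition on objective 10 has no threshold, however, objective 7 has no condition at all, and neither objective has a summary estimate.

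A reader might infer that 32 hazard ratios are each tested at 5%, so that a chance finding is likely. The protocol does not support this. It attaches no test, alpha or decision rule to objectives 7 and 10; the p<0.05 criterion belongs to the study-size simulation for the pooled primary HR. Twenty of the 32 are conditional. The outcomes overlap, since pneumonia sits within the other serious infections and is then split into fatal and non-fatal. Sparse sources also do not behave as full-size 5% tests. Any multiplicity statement or hypothesis-generating label can properly come in the SAP.

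A reader might also infer that the restriction causes the low event counts. It does not: the small sources are small either way, and France dominates with or without pooling.

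Pooling has limits too. Sparse cells may be withheld, and withholding is most likely at the 10% share, where the gain in power is largest. Between-source variance is poorly estimated from four sources, and ascertainment differs between them. These limits argue for a conditional rule, not against pooling.

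**Conclusion.** The point holds as a gap in a stated rule. Under the protocol as written, none of the eight secondary comparisons gets a cross-country estimate. The 24 hazard ratios outside France have at most 0.33 power for HR 1.5 (Schoenfeld; 0.37 by the Wald form). That ceiling does not depend on the assumed sub-type share, because it already grants the whole composite rate; it does rest on the protocol's rates, follow-up and Table 8 counts, and shorter follow-up lowers it.

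The size of the remedy's benefit does depend on the assumed shares and on sparse results being releasable. The main gain is one interpretable estimate per outcome and a check of agreement between sources. The gain in precision over France alone is modest for rare sub-types and about nil for common ones. The plan contains no error of arithmetic or logic here, so this is a worthwhile, inexpensive improvement.

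**What to change.** In section 10.7.1.6, the abstract and Table 2, extend the meta-analysis to objectives 7 and 10 for each outcome where at least two sources give an estimable and releasable log HR and standard error. Use the random-effects inverse-variance model already specified, with the fixed-effect model as sensitivity analysis and the same heterogeneity statistics and forest plot. Name the pooled HR as the summary for each secondary comparison and keep the country HRs as supporting results. Where fewer than two sources qualify, say so and report what is available.

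Do not bring in sources without an estimable HR through crude rate ratios. That would mix estimates lacking the covariate adjustment of section 10.7.1.4 with adjusted HRs, and it needs counts from the very cells that may be withheld.

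The cost is a change of wording and up to eight further runs of a model already planned, with no new data or patients. Pooled estimates for the rarest outcomes, such as fatal pneumonia, will remain imprecise, and the report should say that the pooled value is weighted mainly by France.
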